1.3. Schedule of Activities (SoA)

Study Schedule Protocol I6T-MC-AMBX

Procedure	Screening -28 to -2 days prior to Day 1	Study Day																	Comments
		-1	1	3	5 ±1d	8 ±1d	11 ±1d	15 ±2d	22 ±2d	29 ±2d	36 ±2d	43 ±2d	50 ±2d	57 ±3d	64 ±2d	71 ±3d	85 ±3d or ED		
Informed consent	X																		
Medical history and demographics	X																		
Review and confirm inclusion and exclusion criteria	X	X																	
Admission to CRU		X																	
Discharge from CRU			X																Participants may be discharged after completing the 4-hour safety assessments on Day 1, or later at the investigator's discretion.
Outpatient visit	X			X	X	X	X	X	X	X		X		X		X	X		
Safety assessment (telephone call)											X		X		X				To check on the presence of any AEs and concomitant medications.
Randomization			X																Participants will be randomized 1:1 to 1 of 2 delivery devices and 1:1:1 to 1 of 3 injection locations per delivery device.
Height, weight, and BMI	X																X		Only weight will be measured on Day 85 or ED.
Body temperature	X	X	P	X	X	X	X	X	X	X		X		X		X	X		
Physical examination		X	X														X		Complete physical examination at Screening. Symptom-directed examinations and assessments at other times, and as deemed necessary by the investigator.

Procedure	Screening	Study Day																	Comments
		-28 to -2 days prior to Day 1	-1	1	3	5 ±1d	8 ±1d	11 ±1d	15 ±2d	22 ±2d	29 ±2d	36 ±2d	43 ±2d	50 ±2d	57 ±3d	64 ±2d	71 ±3d	85 ±3d or ED	
Vital signs (pulse rate and blood pressure) (sitting) (hours)		X			P, 2 to 4 h				X				X					X	Day 1: 2- to 4-hour assessment to be conducted at least 2 hours after second injection and prior to discharge at approximately 4 hours postdose. Time points may be added if warranted and agreed upon between Lilly and the investigator.
Clinical laboratory tests	X	X	X				X		X									X	See Section 10.2, Clinical Laboratory Tests, for details.
Serology	X																		See Section 10.2, Clinical Laboratory Tests, for details.
QuantiFERON®-TB Gold test	X																		
Ethanol test and drug screen		X	X																Urine drug test will be conducted at screening and check-in (Day -1). A urine ethanol test will be conducted at screening and a breath-test at check-in on Day -1. Tests may be repeated locally at additional time points at the discretion of the investigator.
FSH	X																		Females only. See Section 10.4.

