4.1. Overall Design

Study AMBX is a Phase 1, open-label, 2-arm, randomized, parallel-design, single-dose, multi-site study in healthy participants.

Screening

All participants will be screened within 28 days prior to enrollment. At screening, participants will be stratified into 1 of 3 weight categories (less than 70 kg, 70 to 80 kg, and more than 80 kg).

Treatment and Assessment Period

Eligible participants will be admitted to the clinical research unit (CRU) on Day -1.

Within the 3 weight categories, participants will be randomized ([Table AMBX.1](#)) using a computer-generated allocation code (Section [6.3](#)):

- 1:1 to delivery device (either PFS [reference] or AI [test])
- within each delivery-device group 1:1:1 to injection-site (arm, thigh, or abdomen)

On Day 1, participants will receive a total of 3 mL (300 mg mirikizumab) as 2 SC injections of 1 mL and 2 mL delivered via PFS or AI in the location assigned by the randomization.

Participants may be allowed to leave the CRU after completing the 4-hour safety assessments on Day 1, or later at the investigator's discretion, and will return for PK and immunogenicity sampling and safety assessments at predefined times up to 12 weeks postdose. Participants will be monitored for safety between outpatient visits by way of telephone assessment.

Safety and tolerability will be assessed through clinical laboratory tests, vital signs measurements, ECGs, recording of adverse events, recording of injection-site reactions, and physical examination.

Table AMBX.1. Study AMBX Stratification and Randomization Plan

Weight Category (Participants) ^a	Injection Device	Subcutaneous Injection Location ^b	Desired Number of Participants
Low <70 kg (~72 participants)	1 x 1-mL + 1 x 2-mL PFS (Reference) or 1 x 1-mL + 1 x 2-mL AI (Test)	Arm	12
	1 x 1-mL + 1 x 2-mL PFS (Reference) or 1 x 1-mL + 1 x 2-mL AI (Test)	Abdomen	12
	1 x 1-mL + 1 x 2-mL PFS (Reference) or 1 x 1-mL + 1 x 2-mL AI (Test)	Thigh	12
Medium 70 – 80 kg (~72 participants)	1 x 1-mL + 1 x 2-mL PFS (Reference) or 1 x 1-mL + 1 x 2-mL AI (Test)	Arm	12
	1 x 1-mL + 1 x 2-mL PFS (Reference) or 1 x 1-mL + 1 x 2-mL AI (Test)	Abdomen	12
	1 x 1-mL + 1 x 2-mL PFS (Reference) or 1 x 1-mL + 1 x 2-mL AI (Test)	Thigh	12
High >80 kg (~72 participants)	1 x 1-mL + 1 x 2-mL PFS (Reference) or 1 x 1-mL + 1 x 2-mL AI (Test)	Arm	12
	1 x 1-mL + 1 x 2-mL PFS (Reference) or 1 x 1-mL + 1 x 2-mL AI (Test)	Abdomen	12

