	1 x 1-mL + 1 x 2-mL PFS (Reference) or 1 x 1-mL + 1 x 2-mL AI (Test)	Thigh	12

Abbreviations: ~ = approximately; AI = autoinjector; PFS = pre-filled syringe.

- a. Approximately equal numbers of participants will be recruited to each weight category.
- b. A dose of study intervention will consist of 2 subcutaneous injections of mirikizumab into the arm, thigh, or abdomen. All doses will be administered by trained site staff.

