4.2. Scientific Rationale for Study Design

CCI

population of healthy participants is frequently used in the assessment of the PK of both small and large molecules.

Single 300-mg doses of mirikizumab and the PK sampling time points have been selected to generate PK profiles sufficient to fulfill the study objectives.

Participants will be randomized to receive injections in the arm, thigh, or abdomen, as injection location has been observed to have an impact on bioavailability in some studies with mirikizumab.

Previous population PK analyses have shown that patients with a lower body weight tended to have a lower clearance and/or central volume of distribution. While the effects of body weight on

these PK parameters were statistically significant, it was not considered to be clinically relevant. However, to mitigate these potentially confounding effects, approximately equal numbers of participants in each weight category are proposed to avoid a large difference in mean weight between the test and the reference delivery-device groups. A participant population of 72 per weight group is an approximate target with the recommended weight categories selected based on the distribution of weights in prior studies. The number of participants assigned to each delivery device and the number of participants assigned to each site of injection is desired to be balanced.

A parallel-group design is chosen because mirikizumab has a half-life of approximately 10 days. Additionally, a crossover study could confound PK data if participants develop neutralizing antidrug antibodies (ADAs).

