9.3.2.2. Pharmacokinetic Statistical Inference

The C_{max} , $AUC(0-\infty)$, and $AUC(0-t_{last})$ will be log-transformed and analyzed using a linear fixed-effects model. The model will include delivery device, injection location, and weight stratification as fixed-effects. The dosing regimen differences between AI and PFS administrations will be back-transformed to present the ratios of geometric LS means and the corresponding 90% CI. Comparisons will be made between the 2 delivery devices and then between the 3 injection locations.

The 2 delivery devices will be considered bioequivalent if the 90% CIs of the ratio of geometric LS means fall within 0.8 to 1.25.

The t_{max} of mirikizumab between AI and PFS administrations will be analyzed using a Wilcoxon rank sum test. Estimates of the median difference, 90% CIs, and p-values from the Wilcoxon rank sum test will be calculated.

Additional PK analyses may be conducted if deemed appropriate.

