## 9.2 Demographics and Participant Disposition

Participant disposition will be summarized and listed. The demographic variables age, sex, race, ethnicity, country of enrolment, site ID, body weight, weight category, height and body mass index will be summarized by treatment and injection site, and listed. All other demographic variables will be listed only.

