#### **9.3.2 Pharmacokinetic Statistical Methodology**

The  $C_{\max}$ ,  $\text{AUC}(0-\infty)$ , and  $\text{AUC}(0-t_{\text{last}})$  will be log-transformed and analyzed using a linear fixed-effects model. The model will include delivery device, injection location, and weight

stratification as fixed-effects. The dosing regimen differences between the AI (Test) and PFS (Reference) administrations will be back-transformed to present the ratios of geometric least squares means and the corresponding 90% CI.

Example SAS Code:

```
proc mixed data=xxx;
by parameter;
class device location strat_weight;
model log_pk = device location strat_weight / residual;
lsmeans device / alpha=0.1 cl pdiff;
ods output lsmeans=lsmeans diffs=diffs;
run;
```

The  $t_{max}$  of mirikizumab between the AI (Test) and PFS (Reference) administrations will be analyzed using a Wilcoxon rank sum test. Estimates of the median difference, 90% CIs, and p-values from the Wilcoxon rank sum test will be calculated.

Additional comparisons will be made between:

- The 2 delivery devices (AI [Test] versus PFS [Reference]) separately at each injection location (injection location will be removed from the model above)
- The 3 injection locations (arm [Test] versus abdomen [Reference] and thigh [Test] versus abdomen [Reference]) separately for each device (device will be removed from the model above)

The 2 delivery devices (AI [Test] versus PFS [Reference]) will be considered bioequivalent if the 90% CIs of the ratio of geometric least squares means of  $C_{max}$ ,  $AUC(0-\infty)$ , and  $AUC(0-t_{last})$  fall within 0.8 to 1.25. CCI

Additional PK analyses may be conducted if deemed appropriate.

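### Adding continuous screening weight to the primary bioequivalence model would narrow the 90% confidence intervals slightly, at almost no cost

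*SAP*

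**What the plan says.** Protocol 9.3.2.2 sets out the primary model: "The model will include delivery device, injection location, and weight stratification as fixed-effects". SAP 9.3.2 implements it as "model log_pk = device location strat_weight / residual" after the statement "class device location strat_weight", so weight is a class variable with three levels.

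The levels are those used for randomisation, "1 of 3 weight categories (less than 70 kg, 70 to 80 kg, and more than 80 kg" (Protocol 4.1). The table footnote there adds: "Approximately equal numbers of participants will be recruited to each weight category". Eligibility sets no limit in kilograms, only a BMI of 18.0 to 32.0 (Protocol 5.1), so the outer two strata are open-ended.

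The reason for stratifying is in Protocol 4.2: "Previous population PK analyses have shown that patients with a lower body weight tended to have a lower clearance and/or central volume of distribution". The same paragraph calls the effects statistically significant but not clinically relevant, and gives no coefficient. It states the aim as avoiding a large difference in mean weight between the device groups.

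Continuous weight is available. The Schedule of Activities has a row "Height, weight, and BMI" marked at screening. SAP 9.2 uses the value descriptively: "body weight, weight category, height and body mass index will be summarized by treatment and injection site". Weight-normalised PK parameters are optional (Protocol 9.3.2.1, SAP 9.3.1).

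**The concern.** The protocol treats weight as related enough to PK to stratify on, but the analysis keeps only the category. A participant of 50 kg and one of 69 kg get the same adjustment. If exposure falls steadily with weight, the part of that relation lying inside the strata is counted as unexplained error.

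What is at stake is the width of the 90% CIs for Cmax, AUC(0-∞) and AUC(0-tlast), all of which must fall within 0.8 to 1.25. The same loss applies to the additional comparisons in SAP 9.3.2: devices within each location, and locations within each device. These rest on about 36 participants per cell (216 / 6). Since weight is recorded anyway, the question is how much precision is given up.

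**Working it through.** **1. The plan's own figure.** Inputs from Protocol 9.5 and SAP 7: 108 per group, CV 40%, true ratio 1.07, limits 0.8 to 1.25, 90% CI.

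- σ² = ln(1 + 0.40²) = 0.1484, so σ = 0.3853
- SE = 0.3853 × √(2/108) = 0.0524
- Normal approximation: (ln 1.25 − ln 1.07)/SE − 1.645 = (0.2231 − 0.0677)/0.0524 − 1.645 ≈ 1.32, giving 90.7%. The lower limit adds nothing material.
- Two one-sided t-tests, integrating over the chi-square distribution of the residual variance: 90.5%

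The stated figure reproduces without any weight term. The SAP model has 216 − 1 − 1 − 2 − 2 = 210 residual degrees of freedom.

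**2. How much weight variance the strata leave.** The documents give no weight distribution. I assumed a normal distribution with mean 75 kg and SD 10 to 15 kg, cut off at 45 and 110 kg (SD 10) or 45 and 115 kg (SD 15), with equal thirds in the three strata. On the log scale:

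| SD | Between strata, B | Within strata, W | Captured, B/(B+W) |
|---|---|---|---|
| 10 kg | 0.0157 | 0.0039 | 80% |
| 15 kg | 0.0256 | 0.0067 | 79% |

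The strata already do most of the work. About 88 to 93% of what remains lies in the two open-ended strata.

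**3. What log weight would add.** The documents give no slope b of log exposure on log weight, so I assumed 0.5 to 1.25. They also do not say whether the 40% CV is before or after weight adjustment, so both readings are shown.

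- *40% is the CV after strata:* variance cut = b²W/σ²
- *40% is total variability:* variance cut = b²W/(σ² − b²B)

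Example with SD 15 kg and b = 1: 0.0067/0.1484 = 4.5% on the first reading, and 0.0067/(0.1484 − 0.0256) = 5.5% on the second.

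| SD, slope | Cut, 40% after strata | Power from 90.5% to | Cut, 40% total | Power, strata → with log weight |
|---|---|---|---|---|
| 10 kg, 0.5 | 0.6% | 90.7% | 0.7% | 91.2% → 91.3% |
| 10 kg, 1.0 | 2.6% | 91.2% | 2.9% | 93.1% → 93.7% |
| 15 kg, 1.0 | 4.5% | 91.6% | 5.5% | 94.6% → 95.5% |
| 15 kg, 1.25 | 7.1% | 92.2% | 9.7% | 96.5% → 97.7% |

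Wider tails (42 to 120 kg) at SD 15 kg and slope 1.25 move the extremes to an 11% cut, 92.5% power on the first reading, and a gain of 1.3 points from 96.8% on the second.

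**4. CI width.** The upper half-width is exp(1.652 × SE) − 1. On the total-variability reading it narrows from 8.92% to 8.89% in the first row of the table and from 7.68% to 7.29% in the last.

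**5. Chance imbalance inside strata.** The within-stratum SD of log weight is √W = 0.062 to 0.082. The between-device difference then has SD √W × √(2/108) = 0.008 to 0.011, about 1% on the ratio at slope 1. With 36 per group it is √W × √(2/36) = 0.015 to 0.019.

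**6. If weight has no effect.** Spending one degree of freedom (210 to 209) leaves power at 90.5%.

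**The case against.** The strongest reply is that nothing here is wrong. Randomisation is stratified by weight, the model carries the stratification factor, and that pairing is standard. The stated aim, to avoid a large difference in mean weight between devices, is met by design. The power claim does not depend on the covariate. Every figure for the gain uses a slope and a weight spread that the documents do not give, and even then the gain is small. A continuous term also imposes one log-linear slope across strata, which the class term does not. All of this stands. The last point limits the benefit rather than the validity: with randomised devices, a poorly fitting slope means less variance removed, not a biased device comparison.

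A reader might infer three stronger things that the documents do not support.

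- *That weight is known to drive exposure in this trial.* Protocol 4.2 reports a tendency in patients that was significant but judged not clinically relevant, and gives no size.
- *That the device ratio is biased.* Stratified randomisation balances weight in expectation, and the CI already reflects chance imbalance. Leftover variance widens the interval, which makes a bioequivalence claim harder to reach, not easier.
- *That the location and device subsets are seriously exposed.* SAP 9.3.2 lists them as additional comparisons, and chance imbalance there is only about 1.5 to 1.9% at slope 1.

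The optional weight-normalised parameters and additional PK analyses do not fully answer the point. In an open-label study, a weight adjustment chosen after the data are seen could not support the primary conclusion.

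**Conclusion.** The point holds as a small, low-cost gain in precision. The primary model discards within-stratum weight information that is already collected. On the assumed slopes and weight spreads, using it would lower residual variance by about 0.6 to 10% (about 3 to 5.5% at slope 1). Power for a single parameter would rise by about 0.2 to 2 points, depending mainly on the slope and on what the 40% CV represents. No validity problem follows, no error rate is affected and no stated figure is wrong. If the true slope is near zero the gain disappears, but so does almost all of the cost.

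**What to change.** Before first participant visit, when SAP Section 3 requires sign-off, keep device, location and weight stratum and add the natural log of screening body weight as a continuous covariate, outside the CLASS statement. Use it for all three parameters, and in the by-location and by-device models. Make the change in Protocol 9.3.2.2 and SAP 9.3.2 together, or record it in SAP Section 11, which now states that there are no changes from the protocol. Say which value is used when weight is repeated under Protocol Section 5; the last value before randomisation would serve.

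The cost is one degree of freedom: 210 to 209 in the primary model, 68 to 67 at each location (72 participants) and 103 to 102 within each device (108 participants). The model also assumes a common log-linear slope within strata. No new data, visits or participants are needed. If the sponsor prefers to leave the primary model unchanged, the same model could be pre-specified as a sensitivity analysis, but the precision gain would then not reach the primary intervals.

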6.3. Measures to Minimize Bias: Randomization and Blinding

This is an open-label randomized study; potential bias will be reduced by central randomization.

On Day 1, participants will be assigned a unique number (randomization number). The randomization number encodes the participant's assignment, within their weight stratification category, to one of the 2 possible delivery devices (PFS or AI) and 3 possible injection sites (arm, thigh, or abdomen), according to the randomization schedule generated prior to the study by the Statistics Department at Labcorp Drug Development. Each participant will be dispensed study intervention labeled with his/her unique randomization number.

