### Treatment and Assessment Period

Eligible participants will be admitted to the clinical research unit (CRU) on Day -1. Within the 3 weight categories, participants will be randomized using a computer-generated allocation code:

- 1:1 to delivery device (either PFS [reference] or AI [test])
- within each delivery-device group 1:1:1 to injection-site (arm, thigh, or abdomen)

On Day 1, participants will receive a total of 3 mL (300 mg mirikizumab) as 2 SC injections of 1 mL and 2 mL delivered via PFS or AI in the location (arm, thigh and abdomen) assigned by the randomization.

Participants may be allowed to leave the CRU after completing the 4-hour safety assessments on Day 1, or later at the investigator's discretion, and will return for PK and immunogenicity sampling and safety assessments at predefined times up to 12 weeks postdose. Participants will be monitored for safety between outpatient visits by way of telephone assessment.

Safety and tolerability will be assessed through clinical laboratory tests, vital signs measurements, electrocardiograms (ECGs), recording of adverse events (AEs), recording of injection-site reactions (ISRs), and physical examination.

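### The tmax comparison ignores weight stratum and injection location; if these explain roughly 10% or more of tmax variance, the rank sum test is conservative and its 90% CI too wide

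*SAP*

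**What the plan says.** **tmax analysis.** Protocol 9.3.2.1 names tmax as the secondary PK parameter. Under protocol 9.3.2.2, tmax "between AI and PFS administrations will be analyzed using a Wilcoxon rank sum test". SAP 9.3.2 says the same, that tmax "will be analyzed using a Wilcoxon rank sum test", and adds the outputs: "Estimates of the median difference, 90% CIs, and p-values from the Wilcoxon rank sum test will be calculated". Neither document names a stratum, block or covariate for this test.

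**Allocation.** SAP section 5 states: "Within the 3 weight categories, participants will be randomized using a computer-generated allocation code". The ratio is 1:1 to device, then 1:1:1 to arm, thigh or abdomen within device. Protocol 6.3 says that the randomization number assigns each participant "within their weight stratification category, to one of the 2 possible delivery devices (PFS or AI) and 3 possible injection sites".

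**Cmax and AUC analysis.** Here the plan uses that structure: "The model will include delivery device, injection location, and weight stratification as fixed-effects" (protocol 9.3.2.2, and likewise SAP 9.3.2).

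No reason is given for treating tmax differently. The device comparisons at each location in SAP 9.3.2 are written as variants of the linear model, so they do not clearly supply a stratified tmax result.

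**The concern.** Device is balanced over weight and location by design, so differences in tmax between sites or weight groups fall about equally on both arms and hardly move the device comparison. The unstratified rank sum test still counts those differences in its null variance. If they are large, the p-value is too big and the interval too wide for what the trial measured.

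Besides Cmax, tmax is the only planned device inference on how fast the drug is absorbed. A conservative test makes a real device difference in tmax harder to detect. In a study hoping to show similarity, a large p-value could then be taken as reassurance.

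**Working it through.** **1. The plan's own figure.** The only stated power is about 90% for Cmax and AUC (protocol 9.5, SAP 7), with 108 per group, CV 40%, ratio 1.07 and limits 0.8 to 1.25.
- Log-scale SD: √ln(1 + 0.4²) = 0.3853.
- Standard error: 0.3853 × √(2/108) = 0.0524.
- Power by two one-sided tests: 90.5% (t-based) or 90.7% (normal).

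The figure reproduces. Nothing comparable is stated for tmax: no power, effect size or interval width.

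**2. Design counts.** Protocol Table AMBX.1 gives 12 per row, with about 72 per weight category over three rows. That implies 12 per device per row: 3 weights × 3 sites × 2 devices × 12 = 216. There are nine weight-by-location strata, each with 12 participants per device.

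**3. Theory.** Let R² be the share of tmax rank variance explained by the nine strata. With device balanced within strata, the true variance of the rank sum is about (1 − R²) times the variance the test uses. At a nominal two-sided 10% level:
- size = 2 × [1 − Φ(1.645 / √(1 − R²))]
- excess CI width = 1/√(1 − R²) − 1

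| Assumed R² | Size | CI coverage | Excess width |
|---|---|---|---|
| 0.02 | 9.7% | 90.3% | 1% |
| 0.05 | 9.2% | 90.9% | 2.6% |
| 0.10 | 8.3% | 91.7% | 5.4% |
| 0.20 | 6.6% | 93.4% | 12% |
| 0.40 | 3.4% | 96.6% | 29% |

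**4. Simulation of size and width.** Assumptions: log-normal tmax, median 5 days, log SD 0.45, observed on the planned visit days with jittered actual times, no device effect. There were 5,000 trials per row for size (standard error √(0.1 × 0.9/5000) = 0.4 points) and 600 for width. The planned interval is taken to be the Hodges-Lehmann interval that goes with the rank sum test. The comparator is van Elteren over nine strata with a stratified Hodges-Lehmann interval.

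| Log shifts: site / weight | R² on this grid | Size, unstratified | Size, stratified | CI width in days, unstratified | CI width in days, stratified |
|---|---|---|---|---|---|
| 0 / 0 | 0.00 | 9.9% | 9.4% | 0.386 | 0.416 |
| ±0.1 / 0 | 0.03 | 10.0% | 10.4% | 0.422 | 0.444 |
| ±0.2 / 0 | 0.09 | 8.7% | 10.1% | 0.432 | 0.394 |
| ±0.2 / ±0.1 | 0.12 | 7.6% | 9.4% | 0.445 | 0.412 |
| ±0.4 / ±0.2 | 0.35 | 3.9% | 9.6% | 0.567 | 0.303 |

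In the first row the stratified interval is 0.416/0.386 − 1 = 8% wider; in the second, 0.444/0.422 − 1 = 5% wider.

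**5. Break-even.** With continuous tmax and no stratum effect, mean widths are 0.207 (unstratified) and 0.213 (stratified) log units, so ranking within strata costs 0.213/0.207 − 1 = 2.9%. Setting 1/√(1 − R²) = 1.029 gives R² = 1 − 1/1.029² = 0.056. Below about 5% to 6%, stratifying does not narrow the interval.

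**6. Power.** For a device shift of 0.15 log units (e^0.15 = 1.16, or 16%), with median 4.5 days, log SD 0.45 and 4,000 trials each:

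| Log shift between neighbouring sites / weight strata | Power, unstratified | Power, stratified |
|---|---|---|
| 0 / 0 | 67% | 66% |
| 0.2 / 0.1 | 64% | 66% |
| 0.3 / 0.1 | 61% | 68% |
| 0.5 / 0.15 | 47% | 67% |

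The end-to-end ratio of tmax across the three sites is e^0.4 = 1.5 in the second row, e^0.6 = 1.8 in the third and e^1.0 = 2.7 in the last.

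**7. Imperfect balance.** With a random 10% of participants lost, unstratified size is 8.6% at ±0.2/±0.1 and 4.6% at ±0.4/±0.2. The stratified test gives 10.3% and 9.8%. The pattern does not depend on exactly filled cells.

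**The case against.** The case for leaving the plan alone has four parts.

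- **No decision uses tmax.** The bioequivalence rule in SAP 9.3.2 covers Cmax and the two AUCs only, and the sample size rests on the same parameters. This stands.
- **No documented effect on tmax.** Protocol 4.2 reports location effects on bioavailability and weight effects on clearance and/or central volume, not on tmax. Protocol 2.2.4 reports no difference in median tmax between treatment arms in two earlier studies, without a breakdown by site or weight. This stands, and it makes the point conditional. The scenarios with a clear power gain need tmax to differ about 1.8-fold or more across sites.
- **The test is not invalid.** If strata matter, its error rate falls below nominal and its interval covers more than 90%. That also stands; this is a question of efficiency and calibration. A reader might infer that the interval is too wide and the p-value conservative under any effect of location or weight. The figures do not support that: at site shifts of ±0.1, size was 10.0% and the unstratified interval was the narrower one.
- **Nine strata are a choice.** Only weight is a stratification factor; location is itself randomized, and 12 per cell is a target. Stratifying by weight alone would also respect the stratified allocation. But the 1:1:1 ratio balances device over location, and the plan already adjusts for both factors in the Cmax/AUC model, so using both for tmax is the consistent choice.

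**Conclusion.** The point holds as a minor, conditional one. The planned tmax test does not use a structure that the design provides and that the neighbouring analyses use. If weight and location explain about 10% or more of tmax rank variance, the test is noticeably conservative and the interval over-covers: at 10% to 40% explained, size is 8.3% down to 3.4% and excess width 5% up to 29%. Below about 5% nothing is gained.

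The explained share, the tmax median, the log SD and all shifts are assumptions, because the documents give none of them for tmax. A reader might also infer that the bioequivalence conclusion or the sample size is at risk. Neither is, because tmax enters neither. The practical consequence is one of reading: a non-significant tmax p-value should not be presented as evidence that tmax is equal, and the interval should carry the interpretation.

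**What to change.** In SAP 9.3.2 and protocol 9.3.2.2, replace the rank sum test of tmax with a van Elteren (stratified Wilcoxon) test over the nine weight-by-location strata. Report a stratified Hodges-Lehmann shift with its 90% CI, built from AI-minus-PFS differences within strata. State that a stratum with participants on only one device contributes nothing. Add a sentence that a non-significant result does not show equal tmax. Changing both documents keeps SAP section 11, which records no changes from the protocol analyses, correct.

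The cost is a few lines of code and one or two sentences in each document. If the strata turn out not to affect tmax, about 1 percentage point of power is lost and the CI is about 2% to 8% wider. No change to sample size, visits or the primary analysis is needed.
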